Malhotra & Baker (2019) highlight that group therapy is an effective method of treatment for a variety of psychiatric and behavioural disorders. They found that it affects patients positively through the Yalom Therapeutic Factors (Yalom & Leszcz, 2020). For example, patients realising that there are others similar to them, improving their self-concept by assisting others and witnessing the success of other group members allows them to envision themselves also succeeding have all been shown to be beneficial. Rørtveit et al. (2021) found that a group program was thought to be an essential part of treatment. Jones (2019) also found that a CBT group intervention showed improvements for the participants and helped them regain control of their eating. Yu et al (2021) compared an online BEG group intervention to a face-to-face group amongst adults and found that the online option was feasible and effective. These studies were undertaken within the adult BED population and no paper was found evaluating the effectiveness or feasibility of a group intervention for under 18s.

Within RISE Eating Disorders Service, based in Coventry and Warwickshire Partnership NHS Trust (CWPT) individuals diagnosed with BED are offered guided CBT self-help based on the book Overcoming Binge Eating by Christopher Fairburn (2013). Due to the growing evidence that group therapy can be beneficial for adults with BED, we aim to explore whether or not this is also effective in under 18s. The large geographical area that the CWPT RISE service covers led us to developing the intervention for online use with the aim of increasing attendance and continued participation. The protocol for this BED group intervention has been developed using the current format for individual interventions based on Christopher Fairburn's book as a guide. The benefits of the research are that people on a waiting list will be offered treatment earlier.

Aims

The aim of our study is to assess whether the group intervention can be delivered per the protocol and obtain feedback from the participants of any recommended amendments/adaptations.

Methods

This research will:

1. Review individuals on the RISE Eating Disorder treatment waiting list for Binge Eating Disorder to assess their suitability for an online group intervention. Individuals will be reviewed in order on the waiting list.
2. A carer information session will be held online to discuss their role throughout the research.

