- Error! Reference source not found.

Upon completion of the group, the participants will be asked to complete the questionnaires again.

Participants will undertake a follow-up appointment face-to-face or online at one month post research intervention to complete the questionnaires again and to assess whether or not they continue to require RISE Eating Disorder Service support. If further support is required from the RISE Eating Disorders service, this will be offered by the team. If a need is identified for support that is not offered by the RISE Eating Disorder service, they will be signposted and/or referred to the appropriate service. If they no longer require treatment and are able to manage their binges, they will then be discharged from the service.

Measures

Questionnaires will be completed at baseline (pre-intervention), at completion of group and at one month post-intervention. Individuals will also be provided with an online feedback form at the end of the last group session to complete anonymously to assess their experience of the group.

The questionnaires used are: Eating Disorder Examination – Questionnaire (EDE-Q), Revised Children's Anxiety and Depression Scale (RCADS) Child and RCADS Parent. These are the standard questionnaires used within the service to monitor eating behaviours and mood. The EDE-Q was chosen over a specific binge eating one as this allows to monitor if the eating behaviours change to a different type of eating behaviour as it measures restriction and binging.

The results will be analysed quantitatively with repeated measures statistical tests. We are looking for the EDE-Q scores to reduce which would suggest a reduction in symptoms. Furthermore, we are monitoring mood through the RCADS to see if there is any change in their mood following the treatment.

The feedback form will be utilised qualitatively via content analysis to highlight any changes that the participants would suggest to the group and the space to express verbally how they experienced the group.

Anticipated impact and dissemination

If effective, the group intervention will be offered as a treatment option to service users from the RISE Eating Disorder Service going forward. The results will be disseminated through scientific papers and conferences. If the intervention is successful it might encourage services from other organisations to adopt this approach.

Ethics/regulatory approvals

Declaration of Helsinki

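### Does reading a fall in EDE-Q scores as fewer symptoms hide a shift from binging to restriction?

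*Protocol*

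**What the plan says.** All the text on the EDE-Q is in the protocol's Measures section. The reason given for choosing it over a binge-specific questionnaire is that "this allows to monitor if the eating behaviours change to a different type of eating behaviour as it measures restriction and binging". On timing: "Questionnaires will be completed at baseline (pre-intervention), at completion of group and at one month post-intervention".

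The next paragraph gives the analysis in one sentence, "The results will be analysed quantitatively with repeated measures statistical tests", and the expected direction in another, "We are looking for the EDE-Q scores to reduce which would suggest a reduction in symptoms". No global score, subscale or item is named, and no threshold is set. The RCADS is to be examined for any change in mood, with no direction stated.

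Three other places bear on the point:

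- **Aims:** "The aim of our study is to assess whether the group intervention can be delivered per the protocol", together with participant feedback on possible adaptations.
- **Group intervention**, on the one-month appointment: "If they no longer require treatment and are able to manage their binges, they will then be discharged from the service". This is a clinical judgement about one person, not an analysed outcome.
- **Anticipated impact and dissemination:** "The results will be disseminated through scientific papers and conferences".

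**The concern.** The reason for choosing the instrument and the stated reading of its result appear to pull apart. The EDE-Q was chosen because eating behaviour might change in kind, with restriction taking the place of binging. The sentence on interpretation looks only for a fall. The plural *scores* allows binging and restriction to be read separately but does not require it, and no passage says how a fall in one with a rise in the other would be read.

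Every participant must have a Binge Eating Disorder diagnosis (Inclusion criteria), and the EDE-Q is the only named questionnaire on eating behaviour. If a paper reported only that EDE-Q scores fell, a reader could not tell whether binging had fallen or whether the shift had occurred. The stake is limited to this secondary symptom reading. The protocol does not tie its conditional statement on offering the group in future to the EDE-Q.

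**Working it through.** The protocol gives no scoring rule, sample size, effect size or threshold for the EDE-Q, so there is no figure to reproduce. Two checks are possible: how ambiguous a merged score would be, and whether the text calls for one.

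**1. Ambiguity if the two components were merged.** Let ΔB and ΔR be the changes in binging and restriction. Each can fall, stay the same or rise, which gives 3 × 3 = 9 patterns. Suppose the result is S = wB·B + wR·R with both weights positive. Then ΔS = wB·ΔB + wR·ΔR can be negative only if at least one component falls.

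| Binging | Restriction | Combined fall possible? | Meaning |
|---|---|---|---|
| fall | fall | yes | less binging, no rise in restriction |
| fall | same | yes | less binging, no rise in restriction |
| fall | rise | yes | shift towards restriction |
| same | fall | yes | binging unchanged |
| rise | fall | yes | binging worse, restriction less |
| same | same | no | |
| same | rise | no | |
| rise | same | no | |
| rise | rise | no | |

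Five patterns allow a combined fall. In 2 of them binging falls with no rise in restriction, in 2 binging does not fall, and in 1 binging falls while restriction rises. So 2 + 1 = 3 of 5 do not show reduced binging without a shift.

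A numerical illustration, with values assumed and not in the protocol: take S as the equal-weight mean, binging going from 4 to 2 and restriction from 1 to 2. S moves from (4 + 1)/2 = 2.5 to (2 + 2)/2 = 2.0, a fall of 0.5, although restriction has doubled. Read separately, the same data give −2 for binging and +1 for restriction, and the shift is plain.

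**2. How far the count depends on its assumptions.** It is a list of possibilities, not a probability, and it requires S to contain exactly these two components with positive weights.

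- If other components also enter the score, they can produce an overall fall under all 9 patterns.
- If binging does not enter the score, a fall in S means a fall in restriction. That leaves 3 patterns, in 2 of which binging does not fall.
- If the two are read separately, all 9 patterns are distinguishable.

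Nor are the 3 patterns of one kind. Where restriction falls and binging is unchanged, a symptom has been reduced, and the protocol's sentence speaks of symptoms, not of binging. The shift that concerns a binge-eating population, binging giving way to restriction, is 1 of the 5. Counting the reverse exchange as well makes it 2.

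**3. Whether the text calls for a merged score.** Measures gives two uses of the instrument in adjacent paragraphs. The first is to monitor a change in the type of behaviour, naming restriction and binging as distinct things measured. The second is to look for scores to reduce. The second uses a plural and hedged wording, and attaches no decision. Nothing withdraws the first. An analyst following both would look at restriction and binging and then at whether scores fell.

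**4. Whether anything would be lost.** The EDE-Q is completed at baseline, end of group and one month. Separate results for the two behaviours at those times (2 × 3 = 6 summaries) need no further data collection.

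**The case for a change.** The best case for a change is that the protocol is not merely silent: it states what a reduction means, and that statement does not mention the shift for which the EDE-Q was chosen. The contrast with the RCADS sharpens this. Mood is watched for change in any direction, while the instrument chosen to catch substitution gets the one-directional sentence. The Background and Rationale also speaks of exploring effectiveness in under 18s, so the symptom reading is not idle, and the results are to be published. One sentence would settle the matter at almost no cost.

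Part of this stands. The protocol does not say that restriction and binging will be reported separately, and a sentence saying so would do no harm. But the interpretive sentence does not exclude the monitoring stated just before it, so this is an incomplete description and not a contradiction. The formal aim is deliverability and feedback, and no efficacy test or success threshold rests on the EDE-Q. Which scores are analysed, and how they are laid out, is commonly settled in an SAP.

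Stronger remedies would go further than the gap. Making binging the deciding result and any overall score merely supportive is a preference among outcomes, not the repair of an error. Describing individual participants who shift, by study identifier, would sit badly with the anonymity commitment under Patient confidentiality, since these are under 18s from one service and the group size is not stated.

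**Conclusion.** No change to the plan follows. A fall in a merged binging-and-restriction result would be ambiguous: 3 of the 5 patterns compatible with it do not show less binging without more restriction. But that count rests on a merging that no passage of the protocol describes. Taken whole, Measures says both that a change of behaviour will be monitored and that scores are hoped to fall, and an analyst acting on both reaches a sound reading. The remaining gap is reporting detail that an analyst would fill sensibly from data already collected at all three time points.

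This conclusion assumes that restriction and binging can be read separately from the EDE-Q, as the protocol's own reason for choosing it implies, and that the report honours that reason. It affects only a secondary reading in a pilot whose aim is deliverability and feedback. No effect on any numerical result can be derived, because the protocol states none.

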Evaluation of Pilot Online Binge Eating Disorder Group Intervention in under 18s.

Short Title: **Evaluation of Pilot Online Binge Eating Disorder Group in under 18s.**

Research Protocol Version 2.1 31/03/2023

IRAS Number

320293

Research Question

Can the guided self-help protocol be delivered as an online group intervention?

Core Research Group

[name], Coventry Warwickshire NHS Partnership Trust and Newman University (Chief Investigator; **email: [contact]**)

[name] [name], Newman University (Study Manager; **email: [contact]**)

[name], Coventry and Warwickshire Partnership NHS Trust

[name], Coventry and Warwickshire Partnership NHS Trust

[name], Coventry and Warwickshire Partnership NHS Trust

[name], Coventry and Warwickshire Partnership NHS Trust

Stakeholders

The following stakeholder groups have been identified:

- RISE Eating Disorder service users (current) who are diagnosed with a Binge Eating Disorder
- RISE Clinicians (including Psychologists, Cognitive Behavioural Therapy Therapists, Dieticians, and Assistant Psychologists)
- Non-client-facing service providers such as Service Managers and Commissioners/members of Clinical Commissioning Groups

Funding

This piece of research is being supported by the RISE Eating Disorder service at Coventry & Warwickshire Partnership NHS Trust and is not externally funded.

Sponsor

Coventry Warwickshire Partnership NHS Trust

Timeline

Start Date: 1st February 2023

Duration: 6 months

Background and Rationale

The National Institute for Health and Care Excellence (NICE) Guidelines (2017) recommend cognitive behavioural therapy (CBT) group therapy as an intervention for Binge Eating Disorders (BEDs). These guidelines do not differentiate between what is offered to adults and what is offered to under 18s for BED. Downey (2014) identified that there is limited research on group interventions for Binge Eating Disorder. Further, BED was only established as a diagnosis in the Diagnostic and Statistical Manual of Mental Disorders 5th Edition (American Psychiatric Association, 2013; DSM-5), which means that research is still in the early stages (Kober & Boswell, 2017).

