3. An online one hour group intervention will be delivered once a week for 10 weeks.
4. Follow-up questionnaires will be distributed to carers 1 month after completion of group.

Participants

Individuals on the RISE Eating Disorders Treatment Waiting List will be reviewed by the RISE clinicians who will be facilitating the group intervention for suitability.

Inclusion criteria

- Diagnosed with Binge Eating Disorder
- Under 18 prior to the group starting
- Speaks English

Exclusion criteria

- If underweight
- If have a serious physical illness
- If pregnant
- Physical Health problems due to eating problem
- If mental health needs to be stabilised
- If significant problem with alcohol, drugs, or repeated self-harm
- Not in a place to start (changes upcoming or ongoing)

Procedure

Individuals from the treatment waiting list meeting the inclusion criteria will be approached by CWPT RISE study team clinicians to ask if they are interested in taking part in the research study. Those who express interest will be offered a face-to-face review appointment with two clinicians, including the chief investigator. If, from the review, it is felt that it is appropriate to offer them the study group intervention, it will be explained to them in detail and they will be handed a Patient Information Sheet (PIS), one for themselves and one for their parent / carer. They will be given a week to decide whether or not they would like to take part in the study after which time a clinician will contact them via telephone to ask them what they have decided and to answer any questions. The chief investigator will ensure that the individual is truly interested in the approach and that there is no coercion. Consent forms will be sent via email, which they will be asked to send back signed electronically and send back via email. Once the individual and their parents/carers have signed the consent forms, the parent /carer will be invited to attend an introductory information session online. This session will explain the principles of the group and how they can support the young person throughout the course of the group. Baseline questionnaires will be completed pre-intervention.

Group intervention

The BEG intervention protocol is a separate attached document. The outline of the group consists of:

- Error! Reference source not found.
- Error! Reference source not found.)
- Error! Reference source not found.
- Error! Reference source not found.

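### The protocol's effectiveness wording goes beyond its deliverability and feedback aims, and one uncontrolled before-after cohort cannot support it

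*Protocol*

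**What the plan says.** The protocol describes the study's purpose in several places.

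- **Research Question:** "Can the guided self-help protocol be delivered as an online group intervention".
- **Aims:** "The aim of our study is to assess whether the group intervention can be delivered per the protocol", together with gathering participants' suggestions for changes.
- **Background and Rationale:** after citing evidence in adults, "we aim to explore whether or not this is also effective in under 18s". The same section reports that "no paper was found evaluating the effectiveness or feasibility of a group intervention for under 18s".
- **Anticipated impact and dissemination:** roll-out is made conditional, in these words: "If effective, the group intervention will be offered as a treatment option to service users from the RISE Eating Disorder Service going forward". This section also plans papers and conference presentations. It adds that, should the intervention succeed, services elsewhere might take it up. Neither *effective* nor *successful* is defined.

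On design, Methods says "Individuals will be reviewed in order on the waiting list" and "An online one hour group intervention will be delivered once a week for 10 weeks". Measures says "Questionnaires will be completed at baseline (pre-intervention), at completion of group and at one month post-intervention", with unspecified repeated measures tests to follow. Measures looks for a fall in EDE-Q, which it takes to suggest fewer symptoms, and watches RCADS for any change in mood. No comparator, randomisation or waiting-list control is described, and no second measurement before treatment.

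**The concern.** The formal statements of purpose and the wording around them do not ask the same question. Whether a group can be run as planned can be answered by running it once and recording what happened. Whether it is effective requires some estimate of what would have happened without it, and this design provides none.

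What is at stake is the conclusion drawn from the results. The protocol found no earlier study of such a group in under 18s and plans to publish. A before-after fall in EDE-Q could then be presented, or read, as the first evidence that the group works in this age range. A statistical analysis plan, if one exists, can name the test and define the change scores. It cannot add a comparator.

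**Working it through.** The plan states no sample size, significance level, effect size or standard deviation, so there is no figure to reproduce. The check consists of comparing the sections and calculating the time span.

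**1. Purpose, section by section**

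| Section of the protocol | What it asks or presumes | Needs a comparison with no group? |
|---|---|---|
| Research Question | Can it be delivered online as a group? | No |
| Aims | Can it be delivered as planned, and what should change? | No |
| Measures | Do EDE-Q scores fall, and does mood change? | No, as worded |
| Background and Rationale | Is it effective in under 18s? | Yes |
| Impact section, service roll-out | Offered further if effective | Yes |
| Impact section, other organisations | Might be adopted if successful | Yes, if success means clinical benefit |

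The first three rows agree with one another. The last three go further.

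**2. What the before-after difference contains**

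For each participant:

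observed change = effect of the group + change that would have occurred without it + measurement error

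With one pre-treatment measurement and no untreated group, the data identify only the sum. The second term may include natural course and regression to the mean. Repeated pre-treatment measurements would give some information on it, and a comparator would estimate it. Neither is planned.

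**3. Time open to untreated change**

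Inputs: 10 weekly sessions (Methods), and questionnaires at the end of the group and one month later (Measures).

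- First to last session: 10 − 1 = 9 intervals of one week = 9 weeks.
- One month: 30.4 days ÷ 7 = 4.3 weeks.
- First session to one-month questionnaires: 9 + 4.3 = 13.3 weeks.

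Both spans are minimums, because the baseline questionnaires are completed before the first session.

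**4. Size of the possible bias**

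This cannot be derived. The document gives no number of participants, no EDE-Q threshold for entry, no test-retest correlation, no named test and no untreated trajectory. A probability of a significant fall with no group effect could be calculated only by assuming all of these, and the answer would follow from the assumptions. None is given here.

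**The case against.** The strongest reply is that the study is labelled a pilot and that its two formal statements of purpose agree. The Background sentence speaks only of exploring. The roll-out sentence is a conditional remark in a section on anticipated impact. This stands in part: the design is right for the stated aims. It does not remove the point, because both statements are current text and the roll-out condition rests on a question the Aims do not ask.

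Second, the Background notes that NICE already recommends group CBT for binge eating disorder without differentiating by age, and that the group's content follows the service's existing individual format. Continuing to offer the group therefore need not depend on causal proof from this cohort. This stands, and it lowers the consequence.

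Third, regression to the mean is not shown. Patients are reviewed in waiting-list order with no EDE-Q cut-off. The exclusions for unstable mental health and for upcoming or ongoing changes may remove some patients at a peak. This also stands: untreated change is possible, but its size and direction are unknown.

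Fourth, how change is reported is often left to an analysis plan, and the remedy does not define what counts as deliverable. Both are fair. The essential addition is the statement that change is not attributable to the group. A criterion for deliverability is a separate matter.

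A reader might also infer that a significant EDE-Q fall triggers adoption, so that the protocol has a calculable false-positive rate. The text does not support that. No sentence ties a test, a p-value or an EDE-Q result to adoption, and Measures describes a fall only as suggesting fewer symptoms.

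**Conclusion.** The point holds as one about the claim and leaves the design untouched. The Background sentence and the two impact sentences rest on an effectiveness conclusion that one treated cohort with a single baseline cannot give. The study can report whether the group was deliverable, what participants would change, and whether scores moved over at least 9 weeks and about 13 weeks. It cannot say why they moved.

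Severity is minor to moderate. The aims can be met, and the problem is limited to the effectiveness wording. No numerical bias is claimed. The conclusion assumes that the study is single-arm, which is inferred because no comparator is described. It also assumes that no earlier scores will be used. The questionnaires are standard in the service, so such scores may exist, but the protocol does not plan to use them.

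**What to change.** Three wording changes to the protocol:

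1. **Background and Rationale:** reword the sentence about exploring effectiveness in under 18s to match the Aims, namely deliverability and participant feedback, with symptom change as exploratory.
2. **Anticipated impact and dissemination:** reword both the *effective* and the *successful* conditions so that the study's conclusion rests on deliverability and feedback, and no effectiveness claim is drawn from the before-after data. Whether the service then offers the group remains for the sponsor to decide.
3. **Measures:** add a statement such as: Changes in EDE-Q and RCADS are exploratory. They will be reported as change from baseline with 95% confidence intervals at the end of the group and at one month, and cannot be attributed to the group because there is no comparator.

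The cost is a more modest claim and possibly a protocol amendment. No new visits or data are needed, and the confidence intervals come from the questionnaires already planned.
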